### 2.8.4.4 Notable Events

Notable events include death, non-fatal SAEs (including infections and rejections reported as SAE) and AEs (including infections and rejections) leading to discontinuation from the study treatment.

#### 2.8.4.5 Vital Signs

Vital signs variables include measurements of oral body temperature, systolic and diastolic blood pressures, pulse and body weight. Vital signs will be examined for abnormal values and change from baseline according to pre-specified clinically notable criteria. Appropriate incidence rates of clinically notable abnormalities (see [Section 4.6.2](#)) will be provided. Further, descriptive statistics of all vital signs variables as well as the changes from baseline will be presented by visit. A by-patient listing of all vital signs (with clinically notable abnormalities being flagged) will be generated.

#### 2.8.4.6 Laboratory Data

Descriptive statistics (mean, standard deviation, minimum, median and maximum) of quantitative laboratory variables, including change from Baseline, will be generated by visit for laboratory parameters. Categorical levels of urinary protein/creatinine ratio (<30, 30 - <500, 500 - <1000, 1000 - <3000, ≥3000 mg/g) will additionally summarized by visit. When there will be multiple observations in the same visit, the worst case will be selected for this visit.

Laboratory results recorded as >n or <n (above or below detection limit) will be either converted to n (if above detection limit) or set to one-half n (if below detection limit) for the purposes of summary statistics (e.g. if <0.2 was reported 0.1 will be used for the analyses). Original raw results will be listed.

Abnormalities according to the clinical notable criteria (see [Section 4.6.1](#)) will be identified and tabulated for each applicable lab parameter. Lipids levels are categorized based on the following criteria per American Heart Association ([Adult treatment panel III 2002](#)). A by-patient listing of individual patient laboratory data will be generated; values outside of clinical notable will be flagged.

- Triglycerides
  - Normal: < 150 mg/dL
  - Borderline high: 150 – <200 mg/dL
  - High: 200 – <500 mg/dL
  - Very high: ≥ 500 mg/dL
- Total cholesterol
  - Normal: < 200 mg/dL
  - Borderline high: 200 – <240 mg/dL
  - High: ≥240 mg/dL
- HDL cholesterol
  - Low: < 40 mg/dL for men, <50 mg/dL for women
  - Normal: 40 – <60 mg/dL for men, 50 – <60 mg/dL for women
  - Optimal: ≥60 mg/dL
- LDL cholesterol
  - Optimal: < 100 mg/dL
  - Near or above optimal: 100 – <130 mg/dL

- Borderline high: 130 – <160 mg/dL
- High: 160 – <190 mg/dL
- Very high:  $\geq 190$  mg/dL
- Total cholesterol /HDL ratio level is defined as
  - Normal: <5
  - High:  $\geq 5$  but  $\leq 7$
  - Very High:  $>7$

Newly occurring abnormalities since baseline will be summarized by treatment for the clinical notable laboratory abnormalities and the following abnormality criteria (AST or SGOT; ALT or SGPT; TBL: total bilirubin; ALP: serum alkaline phosphatase).

- ALT  $> 3 \times$  ULN
- ALT  $> 5 \times$  ULN
- ALT  $> 8 \times$  ULN
- ALT  $> 10 \times$  ULN
- ALT  $> 20 \times$  ULN
- ALT or AST  $> 3 \times$  ULN
- ALT or AST  $> 5 \times$  ULN
- ALT or AST  $> 8 \times$  ULN
- ALT or AST  $> 10 \times$  ULN
- ALT or AST  $> 20 \times$  ULN
- ALT or AST  $> 3 \times$  ULN & TBL  $> 1.5 \times$  ULN
- ALT or AST  $> 3 \times$  ULN & TBL  $> 2 \times$  ULN
- ALT or AST  $> 5 \times$  ULN & TBL  $> 2 \times$  ULN
- ALT or AST  $> 8 \times$  ULN & TBL  $> 2 \times$  ULN
- ALT or AST  $> 10 \times$  ULN & TBL  $> 2 \times$  ULN
- ALT or AST  $> 20 \times$  ULN & TBL  $> 2 \times$  ULN
- ALP  $> 1.5 \times$  ULN
- ALP  $> 2 \times$  ULN
- ALP  $> 3 \times$  ULN
- ALP  $> 5 \times$  ULN
- TBL  $> 1 \times$  ULN
- TBL  $> 1.5 \times$  ULN
- TBL  $> 2 \times$  ULN
- TBL  $> 3 \times$  ULN
- ALP  $> 3 \times$  ULN & TBL  $> 2 \times$  ULN
- ALT or AST  $> 3 \times$  ULN & TBL  $> 2 \times$  ULN & ALP  $< 2 \times$  ULN

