20-Feb-2017	

• Clarified the definition of compliance

• [REDACTED]

• Revised the liver function criteria

• Added that prednisone and equivalent was not used during study as major deviation for PP

• Added the table of selection criteria for FAS and SAF

• Specified HLA mismatch as categorical variable (<math>\leq 3</math> or <math>> 3</math>) in statistical models

• Specified Kenward-Roger method for denominator degrees of freedom in mixed effect model. Used "Study Day" instead of "subject" in the random statement.

• Added dummy code for mixed effect model

• Defined treatment-emergent AE

• Added program specific safety risk events

• Added safety events for clinical trial safety disclosure

• Added notable lab abnormalities in the list of newly occurring abnormality criteria

• Updated the visit windows

• Added details for multiple imputation and the control-based imputation

• Changed Month 1 to Week 4. Changed "subject" to "patient"

27-Feb-2018	

• Added discontinuation reasons hierarchy when several study drugs are affected

• In laboratory assessments, for multiple observations in the same visit window, the worst case is selected

• The last disposition date will be defined as the latest date in the database (across all visit dates itself, all visit related assessment dates, other assessment dates, event dates (start and end), medication dates).

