### 2.1 Data Analysis General Information

The cut-off day is defined as the latest study day before and up to which data will be used in the analysis on an individual patient level. The cut-off date for 12-month analysis will be the day of Month 12 Visit (specifically, Date of Discontinuation/Study Phase Completion as recorded on the Month 12 Disposition eCRF) + 2 Weeks, but no later than Day 450 (upper limit of Month 12 analysis window). For the 24-month analysis, there will be no cut-off day. All data in the clinical database will be used for the analyses.

Data listings will include all data collected up to the cut-off date for the 12-month analysis, or all data recorded in the database for the 24-month analysis.

For summary tables and figures, the following rules will be applied unless otherwise indicated:

- Categorical data will be summarized by frequencies and percentages. Continuous data will be summarized by mean, median, standard deviation, minimum and maximum and the number of non-missing data points.
- All AE/Infection, notable events, CMV information, EBV information and other events of interest will be summarized based on all collected events with onset on or after the first day of study medication up to the cut-off date or seven days after last dose of study medication. For SAE/infection and death, all events will be summarized.
- All lab or vital sign tables will include data up to the cut-off date or two days after last dose of study medication (on-treatment analysis);

- Efficacy and renal function analyses will be primarily based on all available data including those after study medication discontinuation; as a sensitivity analysis they will include only data up to two days after last dose of study medication (on-treatment analysis). Patients will be censored for the time to event analyses if they do not have an event. For on-treatment analysis, the censoring day is two days after discontinuation of study medication or the last contact day, whichever is earlier; for analysis regardless of on-treatment or off-treatment, the censoring day is the last contact day.
- For post-baseline continuous values, for a given patient, if multiple numeric measurements for a given variable are reported within the same visit window (see the definition for visit windows in [Section 4.1](#)), the following rule will be applied:

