  - For quantitative measures including EVR/CsA/TAC trough levels, the closest value to the planned visit (baseline visit: date of transplant; other visits: midpoint of visit window) is taken (if tie, the last will be used).
  - For qualitative (categorical) assessment, the worst value of all records observed in the visit window will be used. An event defined on a quantitative measure is also a qualitative (categorical) assessment. For example, ALT >3x ULN; the highest (worst) value is compared to the ULN.

Details about the definition of efficacy and safety events, data handling conventions including the ‘re-aligned’ visit windows, imputation of missing dates, and other details can be found in the [Section 4](#).

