## 4 Appendix

### 4.1 Visit-Windows

*Visit-windows* will be used to summarize the data by visit and are defined in terms of weeks and months; these will be based on the study schedule of evaluation and comprised a set of days “around” the nominal visits. Visit-windows are non-overlapping; all together they cover the entire study period, e.g., the visit-window *Month 2* comprises study days 45 to 90, i.e., it has the nominal visit Month 2 as “center” and includes the 15 days preceding study day 60 and 30 days thereafter. Generally, visit-windows are not symmetrical around the nominal visit day.

As patients do not necessarily have their examinations at the exact scheduled time, it might be misleading if all data with the same nominal visit number are lumped together for a by-visit analysis. Thus, all data (including reported unscheduled assessments) are “re-aligned” according to the window schema given below. Note that the visit windows defined in the protocol are used to guide investigators whereas the ‘re-aligned’ visit windows in [Table 4-1](#) (simply called visit windows in the following) will be used for the analyses.

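### As written, SAP 2.8.4.6 takes the worst laboratory value per visit for means and changes from baseline, where SAP 2.1 takes the closest, and it gives worst no direction

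*SAP*

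**What the plan says.** SAP 2.1 sets the general rule for repeated values. It opens: "For post-baseline continuous values, for a given patient, if multiple numeric measurements for a given variable are reported within the same visit window". It then separates two cases. For quantitative measures, "the closest value to the planned visit (baseline visit: date of transplant; other visits: midpoint of visit window) is taken", with the last value used in a tie. For categories, "For qualitative (categorical) assessment, the worst value of all records observed in the visit window will be used"; an event defined on a quantitative measure, such as a transaminase above a multiple of the upper limit of normal, counts as a category. These rules give way where another section says otherwise.

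SAP 2.8.4.6 covers laboratory data. It begins: "Descriptive statistics (mean, standard deviation, minimum, median and maximum) of quantitative laboratory variables, including change from Baseline, will be generated by visit". A sentence on urinary protein/creatinine categories follows, and then: "When there will be multiple observations in the same visit, the worst case will be selected for this visit".

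The SAP's document history entry of 27 February 2018 records the addition as "In laboratory assessments, for multiple observations in the same visit window, the worst case is selected".

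Three other provisions bear on the effect:
- SAP 4.1 re-aligns all data into the analysis windows, reported unscheduled assessments included.
- SAP 2.1.1.4 defines baseline as the last non-missing value before randomization.
- SAP 4.2.1.1 takes the closest value when several renal function assessments fall in one window, and SAP 4.2.1.2 refers to the same Section 2.1 guidelines.

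**The concern.** A mean of worst values does not estimate the typical level at a visit. It depends on how many samples a patient happened to give in the window, and it moves to the unfavourable side as that number rises. Change from baseline is affected in full, because the post-baseline value is selected for being bad and the baseline value is not.

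The windows in SAP Table 4-1 also lengthen over the study, so there is more room for repeat values later on. A drift over visits could then reflect sampling rather than the patients.

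Finally, 2.8.4.6 does not say what worst means for an analyte that can be too low or too high. Two programmers following the text could produce different tables.

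What is at stake is how the descriptive laboratory safety tables read.

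**Working it through.** The plan gives no figure for this rule, so there is none to reproduce. The check has three parts.

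**1. Scope of the sentence.** Read narrowly, it belongs to the urinary protein/creatinine categories in the sentence before it, and it agrees with 2.1. Read as the paragraph stands, it also covers the means and changes from baseline. The history entry speaks of laboratory assessments without limiting them to categories, and a category-only rule would have added nothing to 2.1. The wider reading is the more likely one, but the text should settle it.

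**2. Size of the shift.**

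Inputs from the documents are the selection rules above and the windows in SAP Table 4-1 (end day minus start day plus 1):
- Day 4 and Week 1: 5 days each
- Month 2: 90 − 45 + 1 = 46 days
- Month 9: 315 − 226 + 1 = 90 days
- Month 12: 450 − 316 + 1 = 135 days
- Months 18 and 24: 180 days each

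The within-patient SD (σ) and the number of tests per window (k) are not in the documents. The assumption is k exchangeable normal values around the patient's own mean, and results are in units of σ.

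The expected worst of k values lies c_k·σ from the patient's mean, where

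c_k = ∫ x · k · φ(x) · Φ(x)^(k−1) dx.

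For k = 2 this is 1/√π = 0.564; for k = 3 it is 3/(2√π) = 0.846.

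| Values in window (k) | Worst-value shift (σ) | Closest-value shift (σ) |
|---|---|---|
| 1 | 0 | 0 |
| 2 | 0.56 | 0 |
| 3 | 0.85 | 0 |
| 4 | 1.03 | 0 |
| 5 | 1.16 | 0 |
| 6 | 1.27 | 0 |

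The closest value is chosen by date, not by result, so under this assumption its expected shift is zero for any k.

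For change from baseline, the expected value is the true change plus c_k·σ to the unfavourable side. The baseline value is not selected for being bad, so no term cancels this.

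Not every patient will have repeats. A simulation of 200,000 patients per setting, with 1 + Poisson(λ) tests per window, gave:

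| Mean extra tests (λ) | Worst-value shift (σ) |
|---|---|
| 0.25 | 0.13 |
| 0.5 | 0.25 |
| 1 | 0.45 |
| 2 | 0.74 |
| 3 | 0.95 |

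The closest-value rule stayed between −0.003 and +0.002 σ throughout.

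Between arms, the spurious difference is the difference of the two shifts. With equal testing and equal σ it is zero. With λ = 1 against 0.5 it is 0.451 − 0.253 ≈ 0.20 σ; with λ = 2 against 1 it is 0.742 − 0.451 ≈ 0.29 σ. These contrasts are illustrations; the documents give no testing frequency by arm.

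**3. Direction of worst.** SAP 4.6.1 lists both a low and a high notable limit for potassium (3.0 and 6.0 mEq/L), calcium (6 and 13 mg/dL), glucose (45 and 250 mg/dL), platelets (50 and 700 k/mm³) and WBC (2.0 and 16 k/mm³). If a window holds one value near each limit, 2.8.4.6 does not say which to take.

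**The case against.** **The override is permitted.** The rules in 2.1 yield to other sections, so 2.8.4.6 need not be a contradiction. That stands: this is an override, or a rule of unclear scope, and not a proven conflict. Permission does not remove the bias, and 2.8.4.6 does not say that it departs from 2.1.

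**Repeats may be few.** Protocol Table 6-1 ties central laboratory tests to scheduled visits, the extra draws after dose changes are for trough levels, and Table 4-1 has one scheduled visit per post-baseline window. This also stands. The shift applies only to patients with repeat values, and nothing shows how many there are.

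**Unequal testing is not shown.** A reader might infer that the open-label design must produce a false difference between arms. There are reasons to think testing could differ: the everolimus guidance in Protocol Table 5-2 has thresholds for hemoglobin, cholesterol and triglycerides as well as platelets and WBC, while the numeric MPA guidance in Appendix 3 covers only the last two. That makes it plausible, no more. With equal testing the shift largely cancels between arms, although each arm's means and changes from baseline stay biased.

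**Timing and cross-checks.** The last first treatment was on 26 January 2016, so the rule of February 2018 probably bears mainly on the 24-month tables; the lock date is not given. SAP 4.2.3 adds Month 12 and Month 24 endpoint summaries based on the last available value. These are a partial check, but not for the by-visit rows.

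**Conclusion.** The point holds as a minor one. Followed as written, 2.8.4.6 biases by-visit laboratory means and changes from baseline to the unfavourable side, by about 0.56 within-patient SD with two values in a window and 0.85 with three, against zero under the rule in 2.1. These sizes assume exchangeable normal values. Positive correlation between repeats around the patient's mean would shrink them, and retesting prompted by abnormal results would enlarge them. The missing direction for two-sided analytes needs no such assumption.

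A reader might go further and infer that, because creatinine is a laboratory parameter, the rule raises the share of patients with eGFR < 50 and so reaches the primary endpoint. The documents do not support that. SAP 4.2.1.1 and 4.2.1.2 send renal function values for the main and sensitivity imputations to the closest-value rule, and SAP 2.5.3 dichotomizes eGFR only after the continuous value has been imputed. SAP 2.8.4.6 plans no hypothesis test, and the non-inferiority and superiority analyses are untouched. What remains is that a serum creatinine table under 2.8.4.6 could rest on different samples from the eGFR table beside it.

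**What to change.** Reword the sentence in SAP 2.8.4.6 so that:
- the worst value in a window is used only for category and notable-abnormality tables, with the direction stated for each analyte and both directions tabulated separately where there is a low and a high limit;
- all means, SDs, medians and changes from baseline follow the closest-value rule of SAP 2.1;
- serum creatinine follows that rule too, so that it rests on the same samples as eGFR.

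The cost is one reworded sentence, a short direction list that can sit in the SAP 4.6.1 table, and a change to the record selection for the laboratory summaries. No new data are needed.

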### **2.8.5 Safety Events for Clinical Trial Safety Disclosure**

For the legal requirements of ClinicalTrials.gov and EudraCT, at the end of the study, two required tables on treatment emergent adverse events which are not serious adverse events with an incidence greater than 5% and on treatment emergent serious adverse events and SAE suspected to be related to study treatment will be provided by system organ class and preferred term on the safety set population.

If for a same patient, several consecutive AEs (irrespective of study treatment causality, seriousness and severity) occurred with the same SOC and PT:

[figure not shown]
- a single occurrence will be counted if there is  $\leq 1$  day gap between the end date of the preceding AE and the start date of the consecutive AE;
- more than one occurrence will be counted if there is  $> 1$  day gap between the end date of the preceding AE and the start date of the consecutive AE

For occurrence, the presence of at least one SAE / SAE suspected to be related to study treatment / non SAE has to be checked in a block e.g., among AE's in a  $\leq 1$  day gap block, if at least one SAE is occurring, then one occurrence is calculated for that SAE.

- The number of deaths resulting from SAEs suspected to be related to study treatment and SAEs irrespective of study treatment relationship will be provided by SOC and PT.

### **2.9 Pharmacokinetic (PK)/Pharmacodynamic (PD)/PK-PD/Biomarkers Evaluations**

Not applicable.

## 2.12 Interim Analyses

A futility analysis will be performed when approximately 30% of patients have completed 6 months on the study. The futility analysis described in Section 1.4.1 will be based on the study target population, which consists of 6-month completers and remaining about 70% patients to be enrolled.

The futility analysis outlined in this document is not designed to constitute a binding measure.

All analyses will be provided by the CRO independent team to the Futility Review Board. This list of analyses can be amended at the request of the Futility Review Board. Details of the analyses will be specified in the futility analysis RAPs

### 2.12.1 Futility Analysis

Although the primary study endpoint (the composite of tBPAR or eGFR (MDRD4)  $< 50$  ml/min/1.73m^2) is at Month 12, the futility analysis will be based on the endpoint at 6 months. In kidney transplant trials, typically most tBPAR events (e.g. 80% in A2309 study) occur within the first 6 months, and eGFR at Months 6 and 12 are very similar (e.g. in A2309 study, the mean eGFR was 57.2 at Month 6 vs. 56.3 at Month 12 in the everolimus 1.5 mg group). Therefore, it is expected that the 6-month endpoint will be a good predictor of the 12-month endpoint.

The futility of the non-inferiority for the primary endpoint will be assessed via conditional power together with 95% prediction interval. Conditional power is the probability of rejecting the following null hypothesis given the observed data from the futility analysis patients (6-month completers) and assumptions on the data from future patients. In conjunction with the conditional power, a prediction interval will be calculated to estimate the potential treatment effect and its associated precision (See the calculations of the conditional power and prediction interval in [Section 2.12.3](#)).

$H_{01}$ :  $R_{EVR+tCNI} - R_{MPA+sCNI} \geq 0.10$  (non-inferiority margin): the difference in proportion of patients experiencing tBPAR or eGFR (MDRD4)  $< 50$  mL/min/1.73m^2 at 6 months between the everolimus plus reduced CNI ( $R_{EVR+tCNI}$ ) and the MPA plus standard CNI arm ( $R_{MPA+sCNI}$ ) is at least 10%, vs.

$H_{A1}$ :  $R_{EVR+tCNI} - R_{MPA+sCNI} < 0.10$  (non-inferiority margin): The difference in proportion of patients experiencing tBPAR or eGFR (MDRD4)  $< 50$  mL/min/1.73m^2 at 6 months between the everolimus plus reduced CNI ( $R_{EVR+tCNI}$ ) and the MPA plus standard CNI arm ( $R_{MPA+sCNI}$ ) is less than 10%.

For the futility analysis, the incidence rate of the composite endpoint of tBPAR or eGFR (MDRD4)  $< 50$  ml/min/1.73m^2 will be assessed for each arm for the **6-month completers**. The 6-month completers are defined as follows:

- ~30% of the total randomized patients who have reached Month 6 or discontinued from study early (note: For those patients who were beyond Month 6 in the study, tBPAR up to Month 12 and eGFR (MDRD4) at Month 12 will be used instead if they are available at the time of the futility analysis).
- Patients who have not reached Month 6 yet, but have experienced a tBPAR, graft loss or death event.

For the 6-month completers, it is expected that there will be some patients who drop out from the study prior to Month 6 or miss Month 6 assessments. Missing Month 6 eGFR (MDRD4) will be imputed via the following approach, then the eGFR(MDRD4) value will be dichotomized to derive the component of eGFR (MDRD4) < 50 mL/min/1.73m^2.

- Under the assumption of missing not at random (MNAR), patients who lost their grafts will be assigned a value of zero.
- Otherwise, under the assumption of missing at random (MAR), patients who had missing values including those who died with a functioning graft will have a Month 6 eGFR imputed using **multiple imputation** method based on the longitudinal eGFR data at all available time points up to Month 6 and covariates of randomization strata (donor type and CNI), HLA mismatches ( $\leq 3$  vs  $> 3$ ) and induction.

For the remaining 70% of the patients, expected 6-month failure rates will be assumed using the following scenario:

- Same incidence rates as observed from the 30% futility analysis patients (6-month completers)

For completeness, an assessment of non-inferiority (with NI margin = 10%) for the key secondary endpoint of tBPAR, graft loss or death at Month 6, as well as superiority for the primary endpoint of tBPAR or eGFR (MDRD4) < 50 ml/min/1.73m^2 at Month 6 will be provided using the same approach (i.e. conditional power together with prediction interval) and the assumption for the remaining 70% of patients.

The futility analysis described above assumes the data from tacrolimus [REDACTED]. The Independent Review Board may assess the poolability based on the unblinded futility analysis data and request additional analysis in the tacrolimus subgroup if this is indeed needed.

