#### Testing strategy to control type I error:

Event rates will be compared between groups using the following hierarchical testing strategy:

- a. Non-inferiority of EVR+rCNI vs. MPA+sCNI will be evaluated based on the primary endpoint of tBPAR or eGFR (MDRD4)  $< 50 \text{ mL/min/1.73m}^2$  at Month 12 using a 10% non-inferiority margin (see [Section 2.5.2.1](#)).
- b. Non-inferiority of EVR+rCNI vs. MPA+sCNI will be evaluated with a 10% non-inferiority margin for the key secondary endpoint of tBPAR, graft loss or death at Month 12 (see [Section 2.6.2](#)).
- c. Superiority of EVR+rCNI to MPA+sCNI will be evaluated based on the primary endpoint of tBPAR or eGFR (MDRD4)  $< 50 \text{ mL/min/1.73m}^2$  at Month 12 (see [Section 2.5.2.2](#)).

The above hierarchical fixed hypothesis testing procedure will not inflate overall Type I error rate. Therefore, each hypothesis will be tested at the one-sided 0.025 significance level and no multiplicity adjustment is needed. For these statistical tests, one-sided p-values will be presented in the analysis outputs.

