### Non-Binding Futility Stopping Rule

Based on futility characteristics simulations, the futility stopping rule is developed, which is based on the conditional power for the non-inferiority of the composite endpoint of tBPAR or eGFR (MDRD4) < 50 ml/min/1.73m^2. Recommendation to stop the trial due to futility can be considered if the calculated conditional power is  $\leq 2\%$  based on the scenario described in [Section 2.12.1](#).

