### 3 Determination of Sample Size

The sample size for this study was chosen with the goals to (1) have high power to evaluate non-inferiority in both the overall population *and* the TAC alone population and (2) have adequate power to evaluate superiority in the both the overall population *and* the TAC alone population.

With a sample size of n=1020 randomized per arm (EVR, MPA), the study has at least 95% power to demonstrate non-inferiority ( $\alpha=0.025$ , one-sided) in the overall and TAC alone populations at Month 12. There are at least 73% and 63% power ( $\alpha=0.025$ , one-sided) to demonstrate superiority of 7% or more in the overall and TAC alone populations, respectively.

The calculations are based on the following assumptions:

- 80% of patients are randomized to tacrolimus, 20% of patients are randomized to cyclosporine

- 20% and 30% patients are excluded from the PP population at Months 12 and 24 respectively
- For non-inferiority, the event rate in each arm is 50%, based on study results from RAD001A2309 and [Ekberg 2007](#), and the non-inferiority margin for the primary composite endpoint is 10%.
- For the evaluation of superiority, the event rate in the MPA + sCNI arm is 50%.

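### The futility cohort admits patients still short of Month 6 because they have had an event, which inflates both arms' rates and distorts the conditional power

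*SAP*

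**What the plan says.** SAP 2.12.1 builds the 6-month completers from two groups. The first is about "30% of the total randomized patients who have reached Month 6 or discontinued from study early". The second is "Patients who have not reached Month 6 yet, but have experienced a tBPAR, graft loss or death event".

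For everyone else the plan assumes "Same incidence rates as observed from the 30% futility analysis patients (6-month completers"). SAP 2.12.3 takes the observed rate x_i/n_i from this cohort, sets the future rate p_f equal to it, and projects to N = 1020 per arm. It also states that the key secondary endpoint will use raw rates and not Kaplan-Meier estimates.

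The stopping rule rests on the result: "Recommendation to stop the trial due to futility can be considered if the calculated conditional power is" at most 2%. It is labelled non-binding.

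**The concern.** A patient in follow-up who has not reached Month 6 enters the second group on the strength of an event. Another patient randomised the same day and still event-free does not enter; that patient falls into the remaining 70%. Such failures add to the numerator and denominator together, with no matching event-free patients.

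Because p_f is set to the observed rate, the excess is not confined to the interim data. It is projected onto all remaining patients. Nothing in SAP 2.12.3 weights, censors or otherwise corrects for it.

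The effect on the treatment difference can go either way:

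- With equal numbers of early failures, both rates are pulled towards 1, the difference shrinks and conditional power rises.
- With more early failures on everolimus, the difference is exaggerated and conditional power falls.

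At stake is whether the review board sees a reliable figure when the trial is near the non-inferiority margin.

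**Working it through.** **Inputs from the documents.** N = 1020 per arm with 1:1 allocation. The level: "each hypothesis will be tested at the one-sided 0.025 significance level". The margin: "the non-inferiority margin for the primary composite endpoint is 10" percentage points. The planning rate: "For non-inferiority, the event rate in each arm is 50"%. First group: 30% of 1020 = 306 per arm. Accrual (Protocol, Amendment 1): 2037 randomised between 3 December 2013 and 26 January 2016.

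**Plan's own figure first.** The SAP claims: "With a sample size of n=1020 randomized per arm (EVR, MPA), the study has at least 95% power to demonstrate non-inferiority". With the unpooled normal approximation, power = Φ(0.10/√(2×0.5×0.5/n) − 1.96). This gives 99.5, 98.1, 96.6, 95.1 and 92.2% for n = 1020, 816, 714, 653 and 571, in agreement with Protocol Table 9-1 (>99, 98, 97, 95, 92). The documents give no numerical conditional power to reproduce.

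**Patients short of Month 6 (assumption: uniform accrual).** The interval is 784 days, or 26.1 thirty-day months. 2037/26.1 ≈ 78 per month, and 6 × 78 = 468, or about 235 per arm.

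**Formula (SAP 2.12.3, with p_f equal to the observed rates).** With d = p_EVR − p_MPA:

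- SE_full = √[p_EVR(1−p_EVR)/N + p_MPA(1−p_MPA)/N]
- A = −1.96·SE_full + 0.10 − d
- B_i = (N−n_i)·p_i(1−p_i)/N²
- CP = Φ(A/√(B_EVR+B_MPA))

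Adding m early failures to an arm gives p_obs = (306p + m)/(306 + m) and n = 306 + m.

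**Inflation of the rate.** Suppose 5% or 15% of the 235 have already failed, so m = 11.75 or 35.25. A true 50% reads (153+11.75)/317.75 = 51.8% or (153+35.25)/341.25 = 55.2%. With 120 per arm short of Month 6 the range is 51.0–52.8%; with 400 it is 53.1–58.2%.

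**One case in full: true 58% v 50%, with 15% v 8% failed early.**

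- Without the second group: SE_full = 0.0220, A = −0.0431 + 0.02 = −0.0231, √(B_EVR+B_MPA) = 0.0184, CP = Φ(−1.26) = 10.5%.
- With it: m = 35.25 and 18.8; rates 62.3% and 52.9%; d = 9.4 points; A = −0.0371; √(B_EVR+B_MPA) = 0.0179; CP = Φ(−2.08) = 1.9%.

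**Other cases (235 per arm short of Month 6).**

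| True rates, EVR v MPA | Already failed, EVR v MPA | d read as (points) | CP without → with second group |
|---|---|---|---|
| 50 v 50% | 10 v 10% | 0 | 99.9 → 99.9% |
| 50 v 50% | 12 v 7% | 1.7 | 99.9 → 98.6% |
| 55 v 50% | 10 v 10% | 4.6 | 64.2 → 72.0% |
| 55 v 50% | 12 v 7% | 6.2 | 64.2 → 38.1% |
| 59.5 v 50% | 10 v 10% | 8.8 | 1.9 → 4.2% |
| Key secondary, 15 v 10% | 10 v 7% | 6.5 | 96.0 → 56.3% |

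**Check with an explicit event-time curve.** Take 25.8 calendar months, so 79 patients per month and 474 (237 per arm) short of Month 6. Let the fraction of six-month events seen by day t be (1−e^(−t/60))/(1−e^(−3)), which averages 0.72 over 0–180 days. A 12% six-month rate adds 237 × 0.12 × 0.72 ≈ 20 failures per arm.

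- 12% in both arms: a true 50% reads 53.1%.
- True 58% v 50%, early events 12% v 6%: d goes from 8.0 to 9.0 points and CP from 10.5% to 3.4%.
- True 54% v 50%, early events 12% in both: CP goes from 82% to 86%.

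**Chance of meeting CP ≤ 2%** (200,000 simulated looks; 235 per arm short of Month 6; 75% of their six-month events already seen):

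- True 10-point difference: 57% becomes 48% (early-event risk 15% in both arms) or 70% (20% v 10%).
- True 5-point difference: 14% becomes about 11% (15% in both) or 18% (15% v 10%).
- No difference: about 1–2% throughout.

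**The case against.** The strongest reply is that little turns on this number. The rule is non-binding, and Protocol 9.6 has the results weighed together with other efficacy and safety data. The board also receives Kaplan-Meier and full-analysis-set summaries and may ask for more. At the planning assumption of equal 50% rates, conditional power stays near 99% under the scenarios above. The 2% line is crossed only when the true difference is already close to the margin, and the early-event rates used to show this are assumed. All of that stands and limits the impact. None of it corrects the conditional power, because the additional summaries do not feed into it.

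Two qualifications are also right. A death with a functioning graft has its Month 6 eGFR imputed, so it is not automatically a failure on the primary composite. Treating every added patient as a failure is exact for tBPAR and graft loss, and for all three events on the key secondary endpoint, but slightly overstates the primary-endpoint bias. Early discontinuers can also enter before Month 6 without having failed. The wording of the first group leaves open whether they are drawn only from the earliest 30% or from all patients; the outcome selection strictly concerns those still in follow-up.

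Further details are deferred to separate futility documents that cannot be seen here. The SAP version is dated February 2018, after accrual ended, so the look has probably already taken place. That changes the remedy but not the defect.

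**Conclusion.** The concern holds. The cohort definition selects on outcome, biases both event rates upward, and carries that bias into the rate assumed for all remaining patients.

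Under uniform accrual, with 5–15% of the patients short of Month 6 already failed, a 50% rate is overstated by about 2 to 5 points. The direction of the error in conditional power depends on whether early failures differ by arm, so it cannot be called conservative. It is negligible when the arms are truly equal, large enough to cross the 2% line near the margin, and largest for the key secondary endpoint, where every added patient is an event.

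The number short of Month 6 and the share already failed are assumptions; the documents give neither. The Month 12 analysis and its type I error are not affected. This should be corrected, but it does not threaten the confirmatory result.

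**What to change.** Delete the second group from the definition in SAP 2.12.1. Define the futility cohort by time alone: all patients randomised at least 180 days before the data cut, whatever their outcome and whether or not they discontinued. Patients randomised later, with or without an event, belong to the remaining group. State explicitly that early discontinuers are subject to the same date rule.

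The Month 6 analysis window runs to Day 225, so some Month 6 eGFR values may still be pending at the cut. The multiple imputation already specified in SAP 2.12.1 covers these. An alternative is to keep all patients and use a time-to-event or imputation method that retains the event-free ones short of Month 6.

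If the look has been done, recompute conditional power on the date-defined cohort, report it beside the value the board saw, and note the limitation.

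The cost is two lines of SAP text and one filter in the CRO's program. The interim set loses about 20 patients per arm under the event-time curve above (12 to 35 under the wider assumptions), all of them selected on outcome.
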